7.10.2 Participants Who Become Pregnant

If a female participant becomes pregnant after enrolment into the study, the study product will be immediately terminated, the protocol-specified visit schedule will be followed (for participants who choose to be maintained in follow-up), and the participant will be followed until delivery. The participant will be counseled about available options and appropriate referrals will be made depending on the participants' choice. Participants will also be encouraged to disclose their pregnancy results to a trusted adult (not necessarily the parent/ guardian) [See Section 9.3 for more details].

7.10.3 Management of Hepatitis B

Hepatitis B surface antigen and antibody testing will be conducted at screening for all potential participants. All adolescents who are not immune will be vaccinated for hepatitis B prior to enrollment. Participants will receive their first dose when they receive their results during the screening window, followed by another dose after 30 days (ideally at enrolment). The final dose will occur at approximately 6 months after the first dose, once they are enrolled and participating in the study. Potential participants with positive HepBsAg results will be referred for care and treatment of active infection and cannot be enrolled.

If symptoms or signs of clinical hepatitis are present in a participant during the course of the study, the Site Investigator or designee will temporarily hold oral study product and test the participant for hepatitis (including HBsAg plus any other testing indicated by the local standard of care). If hepatitis B infection is confirmed, the participant will be referred for appropriate care.

7.10.4 Participants Who Temporarily Hold or Discontinue Product Use (Initiated by Participant)

For participants who independently choose to discontinue use of the study product (either temporarily or permanently), the protocol-specified visit schedule will be followed (for participants who choose to be maintained in follow-up), with the exception of administration of study product.

7.11 SPECIMEN PREPARATION, HANDLING AND COLLECTION

Each study site will subscribe to the standards of good clinical laboratory practices (GCLP) and site-specific SOPs for proper collection, processing, labeling, transport, and storage of specimens at the local laboratory. All left over samples after testing, will be destroyed.

7.12 BIOHAZARDOUS WASTE

The Principal Investigator will ensure that biohazardous waste will be contained according to institutional, transportation/carrier, and all applicable regulations.

Table1: Schedule of Study Visits and Procedures**Nb. Screening visit (up to -4 weeks); Enrollment (0 weeks); Final visit (52 weeks).**

Visit week	Prior	Screening	Enrolment	4	8	12	24	36	48	Final 52
Obtain written informed consent for screening and enrolment, from participant and his/her guardian		X								
Assessment of understanding for ICF		X								
Identification number assignment		X								
Locator information		X	X	X	X	X	X	X	X	X
HIV pre-and post-test counselling		X	X	X	X	X	X	X	X	X
Eligibility assessment (including review of all screening documentation)			X							
Sexual risk behavior questionnaire			X	X	X	X	X	X	X	X
Acceptability questionnaire				X	X	X	X	X	X	X
Adherence assessment and counselling				X	X	X	X	X	X	
Feedback of DBS or plasma results to those who agree to this.				X	X	X	X*	X*	X*	
Provision of condoms, condom counselling and rest of prevention package (bar PrEP)		X	X	X	X	X	X	X	X	X
Study product supplies and instructions *Only to those who indicate willingness to use.			X	X	X	X*	X*	X*		

Visit week	Prior	Screening	Enrolment	4	8	12	24	36	48	Final 52
Reimbursement	X	X	X	X	X	X	X	X	X	X
Schedule next visit (if applicable)		X	X	X	X	X	X	X	X	*
Focus group (including assent/consent)	X									X
Obtain/update medical history		X	X	X	X	X	X	X	X	X
Conduct physical exam		X	*	*	*	*	*	*	X	*
Incl TS at enrollment and week 48										
Disclose available test results		X	X	X	X	X	X	X	X	X
Provide or refer for contraception		X	X	X	X	X	X	X	X	*
Contraceptive counseling		X	X	X	X	X	X	X	X	X
Record/update AEs including social harms/benefits			X	X	X	X	X	X	X	X
Treat or prescribe treatment		*	*	*	*	*	*	*	*	*
Syndromic treatment for STIs										
Hepatitis B sAb/sAg testing		X								
Hepatitis B vaccination		*	*				*			
HIV serology		X	X	X	X	X	X	X	X	X
Herpes (HSV-2)		X				X			X	
Chlamydia, and Gonorrhea testing.										
Females low vaginal self-swab		X				X			X	
Males Urine										
Serum chemistries		X				X	X	X	X	
Creatinine Clearance										X
ALT/AST serology		X				X	X	X	X	X
Haematocrit				X	X					X
Full Blood count		X				X	X	X	X	
Measurement of study drug levels (DBS and plasma for drug levels)				X	X	X	X #	X #	X #	X #
Measurement of study drug levels by DBS only										X #

Visit week	Prior	Screening	Enrolment	4	8	12	24	36	48	Final 52
Urine pregnancy testing		X	X	X	X	X	X	X	X	X
Urine dip stick testing		X			X	X	X	X	X	
Adherence counseling				X	X	X	X	X		
* IF clinically indicated, per local standard X = Mandatory # = on PrEP										

8 ASSESSMENT OF SAFETY

The Principal Investigator, site investigators and designated clinical staff are responsible for continuous and close safety monitoring of all study participants and for alerting the Safety Monitoring Committee (see Section 10.5), if unexpected safety concerns arise. Study sites will have written procedures for ensuring prompt reporting to the local Independent Ethics Committees, of any unanticipated problems involving risks to study participants or others. Safety of the adolescent participants in this study are of paramount concern.

- Primary safety monitoring and safeguarding of individual study participants is the responsibility of study staff, under the direction of the IoR. The IoR and designated study staff also are responsible for submitting case report forms to the SMC and EAE reports to the DAIDS RSC, such that relevant safety data are available in a timely manner for other study-specific safety monitoring procedures, as follows:
- The DAIDS RSC, DAIDS RAB Safety Specialist, and DAIDS PSB Medical Officers will review all EAE Forms received for PlusPills and follow up on these reports with site staff, the Protocol Team, and drug regulatory authorities when indicated.
- The PSRT will routinely review safety data reports and will meet approximately once per month or as needed via conference call to discuss cumulative study safety data and any potential safety concerns.
- The Study Monitoring Committee (SMC) also will periodically review study data with a focus on performance indicators such as participant accrual and retention, protocol adherence, and data quality. While site staff is not typically involved in these reviews, site staff should be aware that the SMC might make recommendations to DAIDS and/or the protocol team that could affect the study and sites in significant ways. These decisions are based on a detailed review of the available study data and careful consideration of ongoing participant safety and study viability.

This section presents information related to adverse event (AE) reporting and participant safety monitoring in Plus Pills. Please also refer the following resources relevant to AE assessment and reporting:

- DAIDS Table for Grading Adult and Pediatric Adverse Events (Toxicity Table), version 2.0 dated Nov 2014
- Manual for Expedited Reporting of Adverse Events to DAIDS, Version 2 (DAIDS EAE Manual), dated January 2010
- DAERS Reference Guide for Site Reporters and Study

Physicians

- Package Insert for Emtricitabine/Tenofovir Disoproxil Fumarate (Truvada)
- Package Insert for Emtricitabine
- Package Insert for Tenofovir Disoproxil Fumarate

8.1 ADVERSE EVENT PROCEDURES AND REPORTING REQUIREMENTS

An Adverse Event (AE) is defined as any untoward medical occurrence in a study participant, from the time of enrollment through when s/he terminates from the study; it does not necessarily have a causal relationship with the study product. As such, an AE can be an unfavorable or unintended sign (including an abnormal laboratory finding, for example), symptom or disease temporally associated with the use of a study product, whether or not considered related to the product. This definition is applied to all participants beginning from the time of enrollment.

Study site staff will document in source documents and the appropriate AE Log CRF all AEs reported by or observed in enrolled study participants regardless of severity and presumed relationship to study product. The severity of clinical symptoms will be scored using the DAIDS Table for Grading the Severity of Adult and Pediatric AEs, Version 2.0 Dated Nov 2014. The Investigator or designee must determine the severity of the AE and document it on the appropriate CRF (AE Form). Each adverse event that the participant reports will be graded for severity according to the DAIDS grading scale. If not on the grading scale then the following scale will be applied:

- **Mild:** participant was able to perform all normal activities.
- **Moderate:** the participant had to discontinue some activities due to the adverse event.
- **Severe:** the participant was incapacitated by the adverse event and unable to perform normal activities.
- **Life-threatening** participant experienced extreme limitation in activity, significant assistance required; significant medical intervention / therapy required, hospitalisation or hospice - care probable.

An AE **does not** include:

- Pre-existing diseases or conditions present or detected prior to start of study intervention that do not worsen.

- Medical or surgical procedures (e.g. surgery, endoscopy, tooth extraction, transfusion); the condition that leads to the procedure is an adverse event.
- Situations where an untoward medical occurrence has not occurred (e.g. hospitalization for elective surgery, social and/or convenience admissions).

All AEs will be captured regardless of the association or otherwise to the study intervention and reported on the AE CRF in accordance with study specific procedures. All AE reports will contain at least the date the AE occurred, a brief description of the event, the relationship to study intervention, the action taken, the outcome, date resolved, and the severity of the event.

Suspected, Unexpected Serious Adverse Reactions (SUSARS) will also be reported after the protocol-defined AE reporting period, if the study staff become aware of these at any time.

Requirements, definitions and methods for expedited reporting of Adverse Events (AEs) are outlined in Version 2.0 of the DAIDS EAE Manual, which is available on the RSC website at <http://rsc.tech-res.com/safetyandpharmacovigilance>.

The DAIDS Adverse Experience Reporting System (DAERS), an internet-based reporting system, must be used for expedited AE reporting to DAIDS. In the event of system outages or technical difficulties, expedited AEs may be submitted via the DAIDS EAE Form. For questions about DAERS, please contact DAIDS-ES at [contact]. Site queries may also be sent from within the DAERS application itself.

Where DAERS has not been implemented, sites will submit expedited AEs by documenting the information on the current DAIDS EAE Form. This form is available on the RSC website:

<http://rsc.tech-res.com/safetyandpharmacovigilance/>. For questions about expedited reporting, please contact DAIDS RSC [contact].

Designated study staff will submit AE information and any other relevant safety information to the local Ethics Committee(s) in accordance with EC requirements.

Reporting Requirements for this Study

- The SAE Reporting Category, as defined in Version 2.0 of the DAIDS EAE Manual, will be used for this study.
- The study agents for which expedited reporting are required are: Tenofovir and Emtricitabine as a single combined formulation known as TRUVADA.

- AEs and SAEs will be reported throughout the period of trial follow up.

8.1.1 Social Harms Reporting

The study site teams will monitor for and track unanticipated problems related to study procedures and/or to participation in the study, until participants' time of termination from the study. Study site staff will provide clinically appropriate treatment and/or referrals should any such problems occur.

8.2 EXPEDITED ADVERSE EVENTS (EAE)

The expedited AE reporting period for this study is as per the EAE manual, from study enrollment until study completion or discontinuation of the subject from study participation for any reason. After the protocol-defined AE reporting period, unless otherwise noted, only SUSARs as defined in version 2.0 of the EAE manual will be reported to DAIDS if the study staff become aware of the events on a passive basis (from publicly available information).

All unexpected SAEs related to the study product observed in the clinical trial will be reported to the FDA in accordance with 21 CFR 312.32 (IND Safety Reports).

FOR FURTHER DETAILS SEE APPENDIX 16.9

8.3 LOCAL REGULATORY REQUIREMENTS

In addition to submitting EAE information to the DAIDS Safety Office through the Regulatory Support Center (RSC), the investigators will submit AE information in accordance with local regulatory agencies' or other local authorities' requirements.

8.3 (i) Serious Adverse Events (SAEs) are defined by the ICH E2A definition, as described in Version 2 (January 2010) of the *DAIDS EAE Manual*, section 2.1, Seriousness. An SAE is any untoward medical occurrence following any exposure to the study agent that:

- Results in death,
- Is life-threatening, (*The term "life-threatening" refers to an event in which the patient was at risk of death at the time of the event; it does not refer to an event which hypothetically might have caused death if it were more severe.*)

- Requires inpatient hospitalization or prolongation of existing hospitalization, (*Per ICH SAE definition, hospitalization itself is not an AE, but is an outcome of the event.*)

*The following types of hospitalization do **not** require expedited reporting to DAIDS:*

- Any admission unrelated to an AE (e.g., for labor/delivery, cosmetic surgery, administrative or social admission for temporary placement for lack of a place to sleep),
- Protocol-specified admission (e.g., for a procedure required by protocol), or
- Admission for diagnosis or therapy of a condition that existed before receipt of study agent(s) **and** has not increased in severity or frequency as judged by the clinical investigator. (**NOTE:** A new AIDS-defining event in a subject already known to be HIV-infected would be considered an increase in severity of a pre-existing condition [HIV infection] and would therefore be reportable.) Results in persistent or significant disability/incapacity, Is a congenital anomaly/birth defect,
- Clinically insignificant physical findings at birth, including those regarded as normal variants, do not meet reporting criteria. If a clinically significant anomaly is reported, all other findings (including those of no individual significance) should be included in the same report. For example, an isolated finding of polydactyly (extra fingers or toes) or Mongolian spot in an infant with no other findings would not be reported as an SAE, but polydactyly or Mongolian spot occurring with a major cardiac defect would be reported and included in the SAE report.
- Information about congenital anomalies can be found on the Centers for Disease Control and Prevention (CDC) website: <http://www.cdc.gov/ncbddd/bd/monitoring.htm> – Guidelines for Conducting Birth Defects Surveillance, National Birth Defects Prevention Network (NBDPN), Appendix 3.1. Direct link to document: www.nbdpn.org/current/resources/sgm/appendix3-1.pdf. This website listing should not restrict the reporting of anomalies that the site investigator deems important for the sponsor to know. Is an important medical event that may not be immediately life- threatening or result in death or hospitalization but may jeopardize the patient or may require intervention to prevent one of the other outcomes listed in the definition above. Examples include the following: intensive treatment in an emergency room or at home for allergic bronchospasm; blood dyscrasias or convulsions that do not result in hospitalization; development of drug dependency or drug abuse; etc.

9 CLINICAL MANAGEMENT

9.1 TOXICITY MANAGEMENT

Full physical exams will be performed at screening and week 48. Targeted physical exams will be performed at other visits as needed. Clinical symptoms will be systematically assessed in a structured medical history at screening and enrollment, monthly for three months, and then every 12 weeks for the remaining length of the trial (Months 5-12).

In general, all participants who develop a Grade 1 or 2 AE, regardless of relatedness to the study product, may continue use of the study drug per protocol.

Grade 3: Study drug use should be temporarily discontinued in consultation with the PSRT in Participants, who develop a Grade 3 AE or toxicity that is not specifically addressed below regardless of study product relatedness. In general, and unless otherwise decided in consultation with the PSRT, the investigator should re-evaluate the participant at least weekly for up to 2 weeks (or for 2 weeks following the receipt of the results for lab toxicities) to document resolution of toxicity to less than Grade 2. The study drug should be permanently discontinued if improvement to severity \leq Grade 2 cannot be documented within 4 weeks of receipt of the initial result. If study drug use is resumed and the same Grade 3 AE recurs at any time, the IoR/designee must hold product use and consult the PSRT for further guidance on frequency of reevaluation or progression to permanent discontinuation of the study drug.

For all Grade 4 laboratory-identified or clinical toxicities, the study product will be withheld. Laboratory toxicity will be promptly confirmed by repeating the test on an additional specimen, preferably within seven days. If Grade 4 toxicity is also present on repeat testing of additional specimen and is considered to be related to study medication, the study product will be permanently discontinued. Study product may be resumed after resolution to Grade 1 of any Grade 4 laboratory toxicity or clinical event considered to be not related to study product based on the judgment of the Site Investigator after consultation with the PSRT. If the toxicity recurs to Grade 3 or higher after study product is restarted, the study product will be permanently discontinued.

Participants will be asked to report AEs at every study visit. Clinical AEs will be evaluated by the investigator or designee who has clinical qualifications. Any Grade 3 and 4 clinical AEs will be referred

to a Site Investigator at the time of the visit. A back-up coverage schedule will be developed and posted to assure that a study physician or nurse is available at all times.

In addition to the informal safety monitoring done by the Site Investigator and study clinician, the Protocol Safety and Review Team (PSRT) will conduct interim reviews of safety data and study conduct. These reviews will take place approximately every **month**, or as needed. Any discontinuation and potential resumption of study product will be managed in consultation with the PSRT (see section 10.5 for additional detail).

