9.1.1 Nausea, Vomiting, and Diarrhea

Participants with Grade 1 or 2 nausea, vomiting, or diarrhea may be treated symptomatically with hydration, oral antiemetic therapies or antiemetic suppositories at the discretion of the site investigator or designated clinical staff. The site investigator should order any clinically relevant laboratory analyses (per judgment of the site investigator/or designee). Participants should be reminded to take study drug with food.

Participants with Grade ≥ 3 nausea, vomiting, or diarrhea, for which an alternative etiology is not established, must discontinue the study drug temporarily until grade 2 or lower and be treated symptomatically. Should condition(s) not improve to Grade <2 within 7 days, the site investigator/designee should consult the PSRT for guidance on continuing the temporary discontinuation or progressing to permanent discontinuation of study drug. Repeat episodes of these events will be handled independently, and the instruction above will be followed for each event.

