9.1.4 Management of Hypophosphatemia

Grades 1 and 2 hypophosphatemia:

The phosphate should be repeated within 2 weeks of the receipt of any initially abnormal results. Supplemental phosphate should be given with phosphate-rich food or fluid with or without neutral phosphate solution. Other causes of phosphate loss should be evaluated.

Unless other temporary study drug hold requirements apply, study drug need not be held.

Grade 3 hypophosphatemia:

The phosphate should be repeated within 1 week of receipt of any initially abnormal results, and should be accompanied by serum creatinine testing and urine dipstick for protein/glucose. Supplemental phosphate should be given with phosphate-rich food or fluid with or without neutral phosphate solution, and other causes of low phosphate should be investigated. Participants with any of the following results (of tests accompanying the repeat phosphate test) will have study drug held:

- Proteinuria >2+
- Glycosuria >2+

- Creatinine > ULN
- Creatinine clearance <LLN

Participants may continue study drug provided that:

- Study drug hold is not otherwise indicated (e.g., due to the results of creatinine, creatinine clearance, urine protein, and/or urine glucose)
- Phosphate levels will be retested approximately weekly until return to <Grade 2, unless other retesting schedule has been advised by the PSRT

Grade 4 hypophosphatemia:

The phosphate should be repeated within 1 week of the receipt of any initially abnormal results, and should be accompanied by serum creatinine testing and urine dipstick for protein/glucose. Supplemental phosphate should be given with phosphate-rich food or fluid with or without neutral phosphate solution. Other causes of low phosphate should be investigated.

Participants will have study drug held, and the PSRT must be immediately contacted. Phosphate levels will be retested approximately weekly until return to <Grade 2, unless another retesting scheduled has been advised by the PSRT.

Participants may resume study drug, provided that:

- Study drug hold is not otherwise indicated (e.g., due to the results of serum creatinine, creatinine clearance, urine protein, and/or urine glucose)
- The phosphate level has returned to <Grade 2
- A request to resume study drug is approved by the PSRT

PSRT notification should occur for any result >Grade 2 for protein or glucose measured by urine dipstick performed at the time of confirmatory draw for a phosphate level.

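### The general Grade 4 rule in section 9.1 conflicts with 9.1.1 on recurrent nausea, vomiting or diarrhea and with 9.1.4 on confirmed product-related hypophosphatemia, and no order of precedence is stated

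*Protocol*

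**What the plan says.** The general rule is in Protocol section 9.1. Its Grade 4 paragraph opens: "For all Grade 4 laboratory-identified or clinical toxicities, the study product will be withheld". It then makes three further provisions.

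- **Related laboratory toxicity.** The stop is permanent for a Grade 4 result that meets this condition: "also present on repeat testing of additional specimen and is considered to be related to study medication, the study product will be permanently discontinued".
- **Restart.** "Study product may be resumed after resolution to Grade 1 of any Grade 4 laboratory toxicity or clinical event considered to be not related" to product, in the Site Investigator's judgment and after PSRT consultation.
- **Recurrence.** "If the toxicity recurs to Grade 3 or higher after study product is restarted, the study product will be permanently discontinued".

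The Grade 3 paragraph of the same section is limited to participants "who develop a Grade 3 AE or toxicity that is not specifically addressed below regardless of study product relatedness". The Grade 4 paragraph has no such limit.

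Section 9.1.1 deals with nausea, vomiting and diarrhea of Grade 3 or above, so it includes Grade 4. Participants with such an event, "for which an alternative etiology is not established, must discontinue the study drug temporarily until grade 2 or lower". On recurrence: "Repeat episodes of these events will be handled independently, and the instruction above will be followed for each event".

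Section 9.1.4 has product held for Grade 4 hypophosphatemia. Resumption is allowed when phosphate is back below Grade 2, no other reason for a hold exists, and the last condition is met: "A request to resume study drug is approved by the PSRT". It does not mention relatedness, permanent discontinuation or recurrence.

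Section 9.7 lists product-related toxicity as a criterion for permanent discontinuation and refers back to 9.1 as a whole.

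**The concern.** A site with a Grade 4 event of one of these kinds has two texts to follow. In two situations they lead to different ends: permanent discontinuation under one, possible or repeated restart under the other. The usual assumption that a specific section overrides a general one is weak here, because the protocol wrote that exception for Grade 3 and left it out for Grade 4.

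What is at stake is first the consistent handling of severe events in participants aged 15 to 19. Second, continued use after the initial three months and total time on PrEP are primary Use endpoints (Protocol 4.2 and 10.6; SAP, Primary: Use). A stop imposed by one reading and not by the other would enter those endpoints as a difference in use, though it reflects only which text was applied.

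**Working it through.** No sample size, power or error-rate calculation is involved. The check sets the general rule against each specific section on two questions: what happens to a product-related event, and what happens on recurrence after restart.

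| Event and question | Section 9.1, Grade 4 | Specific section | Result |
|---|---|---|---|
| Nausea, vomiting, diarrhea: recurrence at Grade 3 or above | Permanent stop | 9.1.1: new temporary hold for each episode | Explicit conflict |
| Hypophosphatemia: confirmed and related | Permanent stop | 9.1.4: may resume, no relatedness condition | Explicit conflict |
| Nausea, vomiting, diarrhea: related | Restart described only for unrelated events; 9.7 lists product-related toxicity | 9.1.1: temporary hold, no relatedness criterion | Implied conflict |
| Hypophosphatemia: recurrence | Permanent stop | 9.1.4: silent | No conflict on the text |

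**Row 1.** Take a participant with Grade 4 vomiting and no established alternative etiology who restarts product and later has Grade 3 vomiting. Section 9.1 requires a permanent stop; 9.1.1 requires a temporary hold. Both are worded as mandatory, so a site cannot comply with both. The restart level also differs: Grade 1 in 9.1, Grade 2 or lower in 9.1.1.

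**Row 2.** Take a participant whose Grade 4 phosphate is confirmed on a second specimen and judged related. Section 9.1 ends product use. Section 9.1.4 lets the same participant resume once its three conditions are met. The restart level does not conflict: below Grade 2 agrees with resolution to Grade 1.

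**Row 3.** The permanent-stop sentence for related events depends on repeat testing of a specimen, so it does not literally reach a clinical event. The conflict comes from reading the restart sentence together with 9.7.

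**Row 4.** A conflict would arise only if the Grade 3 or Grade 4 text of 9.1.4 were applied afresh to the recurrent event, which it does not say to do.

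**Precedence.** Neither 9.1 nor its subsections, nor 9.7, nor 10.5 ranks these texts.

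**Size for one participant.** Section 7.4 gives the last supply at week 36 and no further product at week 48. These are ceilings that ignore time on hold.

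- Nausea, vomiting or diarrhea can arise at any time. Taking week 8 as an illustration, 48 − 8 = 40 weeks of product are in question.
- After enrollment, serum chemistries are first scheduled at week 12 (section 7.3 and the Schedule of Study Visits). Assuming phosphate is measured with them, 48 − 12 = 36 weeks.
- The Protocol Summary instead schedules product for 52 weeks, which gives 52 − 8 = 44 and 52 − 12 = 40.

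**Size for the cohort.** With 150 enrolled, one participant reclassified moves a crude proportion remaining on PrEP by 1/150 = 0.67 percentage points. The number affected cannot be computed, because the documents give no expected Grade 4 frequency.

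**The case against.** The strongest reply is that the texts can mostly be read together.

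- **PSRT oversight.** Section 9.1 routes any stop or restart through PSRT consultation, and 10.5 gives the PSRT the final determination where resumption awaits it. This makes divergent site decisions less likely, and it stands as mitigation. It does not settle the matter: 10.5 has the PSRT work from Section 9, which is the conflicting text; the recurrence sentence in 9.1 leaves no discretion; and 9.1.1 itself calls for consultation only when improvement is not seen within 7 days.
- **Cumulative reading of 9.1.4.** Resumption is permissive, and a stop required by 9.1 might count as another reason for a hold. That reading is possible. But the examples given there are renal and urine results, and the condition concerns a hold for some other reason, not a permanent stop for the same event. A restart that 9.1 forbids is therefore still open on the wording.
- **Partial overlap in 9.1.1.** The recurrence sentence in 9.1 follows the sentence on restarting unrelated events, while 9.1.1 covers only events without an established alternative etiology. The overlap is partial, and this stands. It is not empty: an event can be judged unrelated with no alternative cause established, and 9.1.1 itself lets participants restart.
- **Immediate action.** Product is held at once under all three texts for the events they cover. This is correct; the difference lies in what follows.

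A reader might infer that both event types have opposite instructions on both questions. The documents do not support that. Section 9.1.4 says nothing on recurrence, and silence is not an opposite instruction. For related gastrointestinal events the conflict is only implied, and the absence of an established alternative etiology is not a finding of relatedness.

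**Conclusion.** The conflict holds in two places: recurrence at Grade 3 or above after restart following Grade 4 nausea, vomiting or diarrhea without an established alternative etiology, and confirmed product-related Grade 4 hypophosphatemia. With no precedence stated, the same participant could be permanently stopped or restarted.

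The case for acting rests on participant safety and consistent conduct. The effect on the primary Use results is probably small: up to roughly 36 to 44 weeks of product for an affected participant, under the timing assumptions above, and probably few such participants among 150.

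It might also be inferred that the primary safety result would change. The documents do not support this for the index event: adverse events are recorded whatever their relationship to product (section 8.1), the safety analysis is a descriptive summary of Grade 2 to 4 events, and the Grade 4 event that starts the sequence is counted under either reading.

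**What to change.** Reconcile sections 9.1 (Grade 4), 9.1.1, 9.1.4 and 9.7. State whether the general Grade 4 rule or the specific section governs nausea, vomiting and diarrhea, and which governs hypophosphatemia, separately for first occurrence, product-related events and recurrence after restart. Say expressly whether the exemption now written for Grade 3 is meant to apply to Grade 4. Fill the silence on recurrence in 9.1.4, and use the same wording in each place. Which clinical rule applies is for the sponsor to decide.

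The cost is a change of protocol wording, with the usual approvals for an amendment. Sample size and analysis methods are unaffected.
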